**PET & EMA sub-study Aims:**

**Aim 1 (PET):** To evaluate the effects of BATA, relative to a comparison treatment, on PET-derived measures of DA functioning during incentive processing. We hypothesize that BATA, but not the comparison treatment, will result in increased phasic striatal DA release but will not influence background DA striatal tone. **Aim 2 (PET):** To evaluate relations between treatment-related changes in fMRI-derived mesocorticolimbic activation and PET-derived DA functioning in the BATA-treated group. We hypothesize that normalization of fMRI-derived mesocorticolimbic activation due to BATA specifically will be associated with increased phasic DA release but no change in background DA tone during incentive processing. **Aim 3 (EMA):** To evaluate if BATA, relative to a comparison treatment, produces improvements in real-world positive affect and the use of BATA skills. **Aim 4 (EMA):** To evaluate relations between treatment-related changes in fMRI-derived mesocorticolimbic activation and real-world positive affect and the use of relevant BATA skills.

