#### **R61 Phase:**

**Aim 1:** To evaluate whether BATA produces changes in neural responses to reward anticipation and reward outcomes using fMRI that exceed changes due to an active comparison treatment, specifically Mindfulness Based Cognitive Therapy (MBCT) and does not impact neural responses to threat. This aim pertains to only the first 60 participants randomized into the study (n=30 to receive BATA and n=30 to receive MBCT).

**Aim 2:** To evaluate relations between BATA dose (treatment duration) and neural target engagement by examining changes in neural response to rewards with mid-treatment fMRI scans 8 and 12 weeks after starting the 15-week treatment.

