### **Optional Sub-study (UNC Only)**

#### *Ecological Momentary Assessment*

Ecological Momentary Assessment (EMA) allows for the acquisition of naturalistic, real-time assessment of participants' self-reported mood, activities, and behaviors. *Study Procedures*-At the first MRI visit in the BRIC, the subject will review the UNC econsent form that contains the description of this EMA portion of the study. They will either choose to participate or not participate by indicating so on the consent (and can only possibly participate if they have an android or iPhone themselves). If they do agree to participate, at the end of the MRI session, the researcher will guide the participant in downloading the app to the participant's smartphone. The researcher will provide orientation to the app and answer any questions regarding the EMA assessments and data collected. The participant will need to provide an email address & password to be able to access the study specific application. MetricWire will then automatically assign them a unique ID. The EMA data (EMA specific questions are attached to the amendment application for review) will be collected over the course of four 5-day blocks (Saturday-Wednesday) following each of four MRI sessions (during weeks 1, 9, 13, and 16, if applicable).

Since the 1st phase of the study entered a R61 no cost extension & due to limited funds, participants no longer received up to 4 scans. Participants received only pre- and post-treatment scans (2 scans total) &

thus only do EMA after pre & post MRI scans. This is true for any participant who signs the UNC consent on or after 11/1/18 as part of R61.

**R33: The study has entered the R33 phase and with funds available, participants will have the option of participating in the EMA portion after the pre and post treatment scan visits as well as after wks 4, 8, and 12 (if applicable) after completing the computer task visit. These participants will follow the same prompt schedule as pre and post scan EMA timepoints.**

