There will be 2 EMA assessments per day on weekdays and 3 per day on weekends. EMA assessments will occur between 9am on Saturday and 9pm on Wednesday, at specified time windows distributed throughout the day (e.g., 4-7pm). No contact will be made on weekdays between working hours of 9-5. Participants who work outside of these hours will be given the option to block off their unavailable work time. At each EMA timepoint, an alert will be sent to the participant's smartphone (iPhone or Android) and they will be instructed to answer questions regarding current affect, anhedonia (both anticipatory and consummatory), stress, cognitions, and recent activities. EMA data will be collected using the *MetricWire* application. All EMA data will be encrypted on participants' smartphones prior to being uploaded to a secure server and downloaded by the researcher to UNC CIDD secure server in the study specific folder.

In this EMA portion of the study, we will be using **Passive Location Tracking (PLT)** to monitor patient movement during the 5 days (Saturday 9am-Wednesday 7pm) after each MRI. PLT allows us to compare distance traveled before and after both treatments as a secondary, exploratory measure of behavioral activation. With PLT, the server pings the subjects phone to collect a specific GPS location to set up a fence and then only when the phone moves outside of this location, will it wake up & send another GPS location back to MetricWire services. PLT uses what they call the **Geofencing API of the Android or iOS** operating system to do the monitoring of location changes by the participant. More specifically, once these fences are set, the app waits for the system to notify it that the device has left the specified fence. At this time, the app wakes up, determines and records its new location, updates the fences to center on its new location and returns to the inactive state.

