## 9 STATISTICAL CONSIDERATIONS

### 9.1 SAMPLE SIZE DETERMINATION

**Aims 1, 2, and 5:** To evaluate whether BATA produces changes in neural responses to reward anticipation and reward outcomes that (1) exceed our *a priori* target engagement criteria; (2) exceed changes due to a comparison treatment; and (3) does not impact neural responses to threat. To evaluate relations between BATA dose and neural target engagement by examining changes in reward responding with fMRI scans 8, 12 and 16 weeks after starting the 15-week treatment.

Power is calculated for Aim 1 fMRI analyses because of its smaller sample, and the Aims that involve all 210 participants will have higher power because of the larger sample and optimized BATA dose. For Aim 1 we will enroll 30 outpatients per group to have complete data from 25 per group. Based on our pilot data demonstrating increased right CN activation during reward anticipation and decreased rACC activation during reward outcomes, we calculated an effect size of approximately  $z=4.1$ . Conservatively, we estimate the effect size for the increased right CN activation and reduced rACC activation will be in the range of  $z = (0.75-1.25)$ . Our models will thus have  $>90\%$  power at  $\alpha=0.025$ .

**Aims 3 and 4:** To evaluate the effects of BATA versus MBCT on anhedonic symptoms, functional outcomes, and behavioral indices of reward sensitivity. Our power analysis addresses the effects of BATA versus MBCT on SHAPS scores (conducted with Gpower) as an ANCOVA with two groups and two timepoints. With 65 subjects per treatment group with complete data at post-treatment,  $\alpha = .05$ , and assumed correlation between assessments of 0.35 (based on preliminary studies), we will have 98% power to detect small ( $f = .2$ ) effects. Pilot data in depressed patients indicated a large effect from pre-to post-treatment ( $d=1.24$ ,  $f = .62$ ), and we are powered to detect these effects. We are 80% powered to detect the interactions with effects as small as  $f = .14$ .

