**PET Power Analyses:** Sample sizes are dictated by the limitations of this funding mechanism, and we note that the majority of published molecular imaging studies have had relatively modest sample sizes. We also note that one advantage of our approach is that both phasic and tonic DA states are acquired during the same scan, thereby allowing for statistical models that use within-subjects variance calculations. Finally, we highlight that the test-retest stability of [11C]raclopride-derived DA binding potentials is very good (ICC = .82 for the NAcc [46]). Our power analysis is based on power to detect group differences in the intra-subject correlation between DA release and change in BOLD signal. Assuming a standard deviation in DA-mediated binding potential changes of 0.3 (approximately 10%), we will be powered to detect a  $>15\%$  change in DA binding (?BP%) with a power of 0.85 and a false discovery rate of 2.5%. This sample size is limited by the funds available through this grant mechanism and the extremely high cost of PET imaging.

*EMA Power Analysis.* Given our sample size, we consider EMA to be preliminary data that may be used to estimate effect sizes for future grant applications that use EMA as an outcome measure for anhedonia clinical trials. Additionally, the proposed structural equation models are very complicated and may need to be adjusted. With the sample size of the R61 phase of the parent grant, the proposed analyses should have medium power (50% or more) to identify paths if the paths correspond to partial correlations of  $|0.10|$  or larger. By continuing to collect EMA data in R33, we hope to increase our sample size and also explore changes after wk 4, 8, and 12 (if applicable) computer tasks, thus EMA is not only linked to pre- and post treatment MRI scan visits.

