**PET Analysis:** The primary PET metrics to be evaluated will be striatal background DA tone and phasic DA release. Study UNC biostatistician will oversee all analyses. UNC will first evaluate the means and standard deviations of PET-derived striatal binding potentials. **Aim 1** (to evaluate relations between BATA response and PET-derived changes in background DA tone and phasic DA release) will be evaluated by extracting the dynamic change in binding potential ( BPND%) before, during and after the task and then comparing these values before and after treatment between treatment groups. **Aim 2** (to evaluate relations between BATA related changes in fMRI and PET-derived background DA tone and phasic DA release) will be addressed by correlations between changes in PET striatal binding potential magnitudes and changes in fMRI.

**EMA: Primary Analyses**-For EMA, the primary variables of interest will be scores on the positive/negative affect and anhedonia items over the assessment periods. Given the longitudinal (i.e., repeated waves of EMA data) and hierarchical (i.e., assessment timepoints nested within individuals) structure of the data to be collected, Hierarchical Linear Modeling (HLM) will be used to analyze EMA data.

Follow-up analyses with the Passive location tracking of MetricWire will evaluate relations between motion tracking, behavioral, brain, and clinical measures of response to both treatments. **Optional EMA enrollment ended with the NCE June 2022 amendment.**

---

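### The EMA power claim of 50% or more at a partial correlation of 0.10 names no level of analysis and fails for person-level paths such as EMA Aim 4, where power is about 12% at best

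*Combined protocol and SAP*

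**What the plan says.** The EMA paragraph of Section 9.1 ties its power to the R61 sample: "With the sample size of the R61 phase of the parent grant, the proposed analyses should have medium power (50% or more) to identify paths" when those paths are partial correlations of 0.10 or more in absolute value. It covers all proposed EMA analyses and excepts none. It does not state alpha, sidedness, the level at which the 0.10 is measured, EMA uptake, or any variance component.

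Other places that bear on it:

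- **R61 size.** Section 3, under R61 Aim 1: "This aim pertains to only the first 60 participants randomized into the study (n=30 to receive BATA and n=30 to receive MBCT". Section 9.1 adds: "For Aim 1 we will enroll 30 outpatients per group to have complete data from 25 per group".
- **EMA uptake.** Section 4.2 makes EMA optional: "They will either choose to participate or not participate by indicating so on the consent". It also requires the participant's own smartphone.
- **Prompts.** Section 4.2: "There will be 2 EMA assessments per day on weekdays and 3 per day on weekends", in five-day blocks from Saturday to Wednesday. R61 participants had up to four blocks, or two if they consented at UNC from 1 November 2018.
- **Aims.** EMA Aim 3 compares BATA with the comparator on improvement in real-world affect and skill use. EMA Aim 4 in the Synopsis is: "To evaluate relations between treatment-related changes in fMRI-derived mesocorticolimbic activation and real-world positive affect and the use of relevant BATA skills".
- **Model.** Section 9.1 describes the proposed models as structural equation models that may need adjusting. Section 9.2, under the primary EMA analyses, says: "Hierarchical Linear Modeling (HLM) will be used to analyze EMA data".

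**The concern.** A partial correlation of 0.10 is small, and 60 people are few. If the unit is the person, no conventional test reaches 50% power in that setting. Aim 4 has that form: each participant supplies one pre-to-post change in activation, and further phone prompts do not create further fMRI changes.

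The paragraph gives the purpose of EMA as estimating effect sizes for future grant applications. A reader who takes the figure at face value would think Aim 4 has about four times the power it has, and could give a null association between fMRI change and EMA change more weight than it deserves. The power text and the analysis text also name different models, so it is unclear which analysis the figure describes.

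**Working it through.** **Inputs.** r = 0.10 (Section 9.1). n = 60 randomised in R61 and 50 expected complete (Sections 3 and 9.1). Two-sided alpha of 0.05 is an assumption; Section 9.1 uses 0.05 for parent Aims 3 and 4 but gives none for EMA. Prompts per block: 2 weekend days × 3 + 3 weekdays × 2 = 12.

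**1. The stated figure with persons as the unit.** Power is Φ(δ − 1.96) + Φ(−δ − 1.96), with δ = atanh(0.10) × √(n − 3) and atanh(0.10) = 0.1003.

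| n | δ | Power |
|---|---|---|
| 60 | 0.758 | 11.8% |
| 50 | 0.688 | 10.6% |
| 210 (all randomised) | 1.444 | 30.3% |

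The stated 50% is not reproduced. It needs n = (1.96 / 0.1003)² + 3 ≈ 385. Other choices of alpha do not rescue it at n = 60: 18.7% one-sided at 0.05, 19.6% two-sided at 0.10, 30.0% one-sided at 0.10. Counting 240 person-by-scan records (60 × 4) as independent gives 33.9%.

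**2. What the person-level sample can detect.** r = tanh(1.96 / √(n − 3)) for 50% power, and tanh((1.96 + 0.842) / √(n − 3)) for 80%.

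| n | r at 50% power | r at 80% power |
|---|---|---|
| 60 | 0.25 | 0.35 (0.355 to three places) |
| 50 | 0.28 | 0.39 |

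**3. Whether repeated prompts help Aim 4.** Two blocks give 24 prompts per person and 60 × 24 = 1,440 in all; four blocks give 48 and 2,880. For a predictor that varies only between people, divide by the design effect 1 + (m − 1) × ICC. Reaching an effective 385 requires ICC ≤ (1,440/385 − 1)/23 = 0.12 with two blocks, or (2,880/385 − 1)/47 = 0.14 with four. The documents give no ICC. At an assumed 0.3 to 0.5, power runs from 27% down to 19% with two blocks and from 28% down to 19% with four.

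**4. Where the claim can hold: within-person paths.** With prompts as the unit, less one degree of freedom per person, 1,440 − 60 = 1,380 gives 96%, and 2,820 gives nearly 100%. At an assumed 40% prompt completion with two blocks, 576 − 60 = 516 gives 62%.

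**5. Where the claim can hold: arm-by-time (Aim 3).** Suppose 0.10 is an observation-level partial correlation for the arm-by-time term. With arm and time coded ±0.5, the product term has SD 0.25. The arm difference in change is then (0.10/√0.99)/0.25 = 0.402 prompt-level residual SDs. With pre and post blocks of 12 prompts, 30 people per arm, and between-person variance in change equal to q times the prompt-level residual variance, SE = √[(q + 2/12) × 4/60].

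| q (assumed) | SE | 0.402/SE | Power |
|---|---|---|---|
| 0 | 0.105 | 3.81 | 97% |
| 0.1 | 0.133 | 3.02 | 85% |
| 0.3 | 0.176 | 2.28 | 63% |
| 0.5 | 0.211 | 1.91 | 48% |

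This assumes that all 60 take part and answer every prompt.

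**The case against.** The best defence is that the R61 sample size fixes the number of people, not the unit of analysis. EMA data are prompts nested in people, and Section 9.2 says so. On that reading 0.10 may be a prompt-level correlation, and steps 4 and 5 show that the claim can then be met. This stands for within-person paths and, conditionally, for Aim 3. It does not stand for Aim 4 without a low ICC that the plan never states, and the sentence makes no exception for Aim 4.

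A reader might go further and infer that both EMA aims have a flat 12% power because both are between-person comparisons. The documents do not support that. Aim 3 concerns differential improvement, which under a hierarchical linear model is an arm-by-time term. More prompts reduce the error in each person's change and so raise its power. The 12% applies to Aim 3 only if 0.10 is a person-level correlation, which Section 9.1 does not say.

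A reader might also infer that the structural equation models were dropped, so that the power belongs to an analysis no longer planned. Section 9.1 calls them proposed and open to adjustment, and Section 9.2 gives no separate method for Aim 4. The two sections are unreconciled; neither shows that one model has replaced the other.

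The objection that little depends on the sentence is fair. EMA is optional and listed with the secondary and exploratory endpoints, and the go/no-go decision rests only on the fMRI region-of-interest analysis.

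**Conclusion.** As written, the claim is wrong for person-level paths and unspecified for the rest. For Aim 4, power at r = 0.10 is about 12% with 60 people and 11% with 50, against a stated 50% or more. This rests on an assumed two-sided alpha of 0.05, but no conventional alpha closes the gap. The 12% is a ceiling for R61, since EMA is optional and not all 60 are expected to have complete data. The Section 3 text of EMA Aim 4 breaks off in the copy reviewed, so its population cannot be confirmed; if it covers one arm of 30, power is about 8%. Continued EMA collection in R33 could raise the number, but even all 210 would give only about 30%.

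For Aim 3 no single figure is defensible. Power could be well above 50%, or below it once between-person variance in change reaches about half the prompt-level variance. The point is worth correcting because the correction is cheap, but its effect on the trial's conclusions is modest.

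**What to change.** In Section 9.1, replace the EMA power sentence with wording such as:

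> At two-sided alpha 0.05, person-level paths (e.g. fMRI change with EMA change) have at most about 12% power at a partial correlation of 0.10 with 60 participants (about 11% with 50); the correlation detectable with 50% (80%) power is about 0.25 (0.35) with 60 and 0.28 (0.39) with 50.

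Confine any claim of 50% or more to within-person or arm-by-time effects. State with it the level at which 0.10 is measured, the expected number of EMA participants, the assumed prompt completion and the variance components. Then reconcile the structural equation models in Section 9.1 with the hierarchical linear model in Section 9.2, and say which model serves Aim 4, so that the power statement refers to the analysis that will be run.

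The cost is a few sentences of protocol and SAP text. No design, sample size or data collection changes; the stated power for Aim 4 becomes less favourable.

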## 9.2 DATA ANALYSES & STATISTICAL CONSIDERATIONS

fMRI Analyses for Go/No-Go Decision for phase II (R33): Analyses of target engagement will focus on activation in the right CN during reward anticipation, the rACC during reward outcomes, and bilateral amygdala in response to threat. The decision to proceed to the R33 phase will rest on reward-related activation metrics from functional CN and rACC regions of interest (ROIs) derived from our preliminary studies (from [37]). We will make these functional ROIs publically available through the UNC BRIC's website for use by other researchers. Amygdala activation during the threat task will be evaluated using an amygdala ROI defined from the Harvard-Oxford subcortical structural probabilistic atlas. Data will be preprocessed using FSL (Oxford University, UK) as described in our work. We will ensure groups do not differ in head motion by calculating mean framewise displacement which yields, for each participant, a value indicating mean head displacement from one volume to the next. Hypotheses will be evaluated with a ROI approach whereby signal intensities are extracted from ROIs for the relevant task contrasts (i.e., potential win versus non-win trials during MID reward anticipation trials; wins versus non-wins during MID reward outcome trials; fearful and angry faces > shapes during the threat task). **Our go/no-go decision will be based solely on this ROI analysis.**

Exploratory Whole-brain Activation Analyses ROI analyses will be followed-up with whole-brain analyses that will yield activation maps thresholded at a False Discovery Rate of 0.01 to allow for an examination of activation in other reward processing regions, including the ventral striatum/nucleus accumbens, putamen, ventral tegmental area, and orbitofrontal cortex. To optimize BOLD signal coverage in the ventral tegmental area we will acquire high-resolution T1-weighted images with 1x1x1 mm voxel size to allow for precise registration and will use cardiac and respiratory gated imaging during the acquisition of structural scans to address pulsatile artifacts using retrospective corrections implemented with the FSL PNM toolbox.

Exploratory Connectivity Analyses: Mesocorticolimbic connectivity in central to anhedonia. We will explore task-dependent correlations between ROIs using a psychophysiological interactions approach as in our prior work. Timeseries will be extracted from ROIs using FSL Featquery for each participant and trial type and correlation values will be transformed using a Fisher r-to z transformation. We also conduct whole-brain connectivity analysis, with a particular emphasis on the salience network (i.e., dorsal anterior cingulate cortex, anterior prefrontal cortex, and anterior insula), by segmenting the brain based on a probabilistic atlas, while correcting for multiple comparisons at the familywise error rate of  $p < .05$ .

**Secondary Analysis:** Secondary data analysis will be conducted examining relationship between psychological symptoms and patterns of brain activation in the functional neuro data. Data will be transferred from UNC to Duke to be analyzed by Duke study team members.

**Aims 1 and 5:** Only patients who complete baseline measures will receive BATA, and those who complete at least one BATA session will participate in post-treatment assessments (ITT, estimating ~90% of sample). We will compare fMRI activation in regions of interest at pre- and post-treatment. Primary analyses will address changes in regional brain activation from baseline to post-treatment.

Models will include motion parameters, gender, and age as covariates. The design is a 2 (BATA vs MBCT) X 3 (CN, rACC, amygdala) X 2 (pretreatment vs post-treatment) ANCOVA testing the change from pre- to post-treatment as moderated by treatment group and brain region in the outcome variables controlling for the covariates. Post-hoc comparisons will compare change across each region. Note that CN and rACC activation values are derived from the MID task whereas amygdala activation values are derived from the threat task.

**Aim 2:** We will analyze whether dose moderates treatment response via regression models that predict change in neural target (CN and dACC) activation from the number of sessions as an indicator of BATA dose. Hierarchical linear modeling where time-in-weeks is treated as a continuous variable nested within subject will provide parameter estimates of the linear, quadratic, and cubic functions for change over time in neural target engagement over the course of treatment. Standard evaluation (e.g., significant at  $p < .05$ ) will guide our selection of the most appropriate function. From these functions, we can estimate both the point in time where the change in target engagement is greatest and where it approaches 0, meaning minimal further improvement is anticipated. Although mid-treatment scans will occur at weeks 8 and 12, we will estimate change continuously so the optimal dosage is not restricted to one of those timepoints.

**Aims 3 and 4:** To evaluate the efficacy of BATA, relative to MBCT, for treating anhedonia, functional outcomes, and behavioral indices of reward sensitivity, we will test for differential change over time between those who receive BATA and those who receive MBCT post-treatment. We will use an intent-to-treat (ITT) analysis for patients who receive BATA relative to those who don't. The ITT model will be a repeated-measures ANCOVA with effects for treatment condition (BATA, MBCT), outcome measure (SHAPS, PRT, etc), time (pre-treatment, post- treatment) and their interactions. The interaction tests will assess mean differences at each time point as well as differences in the degree of change between the groups. This also provides tests of each group relative to their baseline scores. We will include gender and age as covariates in these models. \*\*We will also note any participants who were enrolled in the study and had PRT & EffRT reward tasks data omitted during COVID-19 times.

**PET Analysis:** The primary PET metrics to be evaluated will be striatal background DA tone and phasic DA release. Study UNC biostatistician will oversee all analyses. UNC will first evaluate the means and standard deviations of PET-derived striatal binding potentials. **Aim 1** (to evaluate relations between BATA response and PET-derived changes in background DA tone and phasic DA release) will be evaluated by extracting the dynamic change in binding potential ( BPND%) before, during and after the task and then comparing these values before and after treatment between treatment groups. **Aim 2** (to evaluate relations between BATA related changes in fMRI and PET-derived background DA tone and phasic DA release) will be addressed by correlations between changes in PET striatal binding potential magnitudes and changes in fMRI.

**EMA: Primary Analyses**-For EMA, the primary variables of interest will be scores on the positive/negative affect and anhedonia items over the assessment periods. Given the longitudinal (i.e., repeated waves of EMA data) and hierarchical (i.e., assessment timepoints nested within individuals) structure of the data to be collected, Hierarchical Linear Modeling (HLM) will be used to analyze EMA data.

Follow-up analyses with the Passive location tracking of MetricWire will evaluate relations between motion tracking, behavioral, brain, and clinical measures of response to both treatments. **Optional EMA enrollment ended with the NCE June 2022 amendment.**

---

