**Aims 1 and 2 pertain to the first 60 participants randomized (n=30 to receive BATA and n=30 to receive MBCT).**

Aim 1: We predict that BATA will increase right caudate nucleus (CN) activation during reward anticipation and decrease rostral anterior cingulate cortex (rACC) activation during reward outcomes, and that BATA will not decrease amygdala activation to threat, confirming the specificity of BATA to these positive valence neural systems.

Aim 2: We predict that the BATA group will show increased right CN activation during reward anticipation and decreased rACC activation during reward outcomes that will plateau after the optimal dose of the intervention has been delivered.

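### The Aim 2 dose analysis names the dACC as a neural target, but the Aim 2 hypothesis and the functional ROIs name the rACC

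*Combined protocol and SAP*

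**What the plan says.** The Aim 2 paragraph of Section 9.2 is the only place where the dose analysis is specified with named regions. Its first sentence sets up regressions that "predict change in neural target (CN and dACC) activation from the number of sessions as an indicator of BATA dose". The next sentences describe a hierarchical linear model over time in weeks, with linear, quadratic and cubic terms. From that model the plan will estimate when target engagement changes fastest and when it levels off. Those sentences mention neural target engagement but name no region, so they take their region from the first sentence.

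The Aim 2 hypothesis in Section 4.1 is that the "BATA group will show increased right CN activation during reward anticipation and decreased rACC activation during reward outcomes that will plateau" once the optimal dose has been given. The same section spells out the abbreviation under Aim 1, where BATA is predicted to "decrease rostral anterior cingulate cortex (rACC) activation during reward outcomes".

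The go/no-go paragraph of Section 9.2 says that target-engagement analyses focus on "activation in the right CN during reward anticipation, the rACC during reward outcomes, and bilateral amygdala in response to threat". It rests the decision to proceed on "reward-related activation metrics from functional CN and rACC regions of interest (ROIs) derived from our preliminary studies". Section 9.2.2 repeats this text. The model for Aims 1 and 5 is a "2 (BATA vs MBCT) X 3 (CN, rACC, amygdala) X 2 (pretreatment vs post-treatment) ANCOVA".

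**The concern.** The Aim 2 sentence is an operative analysis instruction, not background. An analyst who follows it to the letter looks for change in the caudate and in a region labelled dACC. The hypothesis that this analysis is meant to test concerns the caudate and the rACC. The cingulate half of the prediction then has no matching analysis, and the region that is named has no stated prediction.

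Aim 2 is one of the two named aims of the R61 phase. Section 4.3 describes its modelling as the means of estimating how many sessions are needed for target engagement. Because the model sentences inherit their region from the first sentence, the mismatch reaches the estimated time course and plateau as well as the regression on number of sessions.

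**Working it through.** No figure in the plan depends on this point, so there is nothing to recompute. The check is a comparison of every place where the documents name a cingulate region.

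**Places that name the rACC**
- Section 4.1, Aim 1 hypothesis: rACC, expanded as rostral anterior cingulate cortex, decreasing during reward outcomes.
- Section 4.1, Aim 2 hypothesis: rACC, decreasing during reward outcomes and then levelling off.
- Section 4.1, Aim 5 hypothesis: rACC, same direction and task phase.
- Section 9.1, power text headed Aims 1, 2 and 5: pilot data and assumed effects for the right CN and the rACC.
- Section 9.2, go/no-go paragraph: rACC as a focus of target engagement and as a functional ROI. Section 9.2.2 repeats it.
- Section 9.2, Aims 1 and 5 model: rACC as one of three regions.

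**Places that name the dACC or dorsal anterior cingulate**
- Section 9.2, Aim 2 analysis: dACC, abbreviation not expanded.
- Section 9.2, exploratory connectivity paragraph: dorsal anterior cingulate cortex, spelled out, as one node of the salience network in an atlas-based whole-brain connectivity analysis.

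**Are the two labels synonyms?** The plan gives no support for that. It defines rACC as the rostral region and refers to the dorsal region separately, in the connectivity paragraph. The natural expansion of dACC is the dorsal region.

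**Can the sentence be carried out as written?** For the rACC, Section 9.2 supplies a functional ROI from the team's preliminary studies, a task phase (reward outcomes) and a contrast (win against non-win outcome trials). Section 4.1 supplies a direction (decrease). For the dACC as an activation target, none of these four items is given. The connectivity analysis does not fill the gap: it is exploratory, it concerns connectivity rather than activation, and it is not tied to Aim 2.

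**How far does it reach?** The CN is named consistently, except that the Aim 2 sentence omits that it is the right CN. The go/no-go decision uses the CN and rACC ROIs. Aims 1 and 5 use the CN, rACC and amygdala. Aims 3 and 4 use symptom, functional and behavioural outcomes. Only the cingulate half of Aim 2 is affected.

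**The case against.** The strongest reply is that the rest of the plan already resolves the matter. The sentence speaks of the neural target, and Section 9.2 states elsewhere that target-engagement analyses focus on the right CN and rACC. The Aim 2 hypothesis and the power text that covers Aim 2 say the same. On that reading, dACC is a one-letter slip. This is probably right, and it limits the seriousness of the point. It does not remove it, because the error stands in the one sentence that tells the analyst what to model, and the dorsal region is a real entity elsewhere in the same section.

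It can also be said that little now hangs on the dose analysis. Section 6.1.1 records that the R33 duration stays at 8 to 15 weeks, and mid-treatment scans stopped for participants who consented at UNC on or after 11/1/18. That is correct. What remains at stake is the analysis and reporting of Aim 2 itself.

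A reader might go further and infer that the plan leaves a free choice between two cingulate ROIs after the data are seen, with a calculable rise in false-positive risk. The documents do not support this. Only the rACC has a defined ROI, so there are not two specified candidates to choose between. No significance level is stated for the regression on number of sessions; the threshold of .05 in that paragraph guides the choice among linear, quadratic and cubic functions. Any error rate would also need an assumption about how the two regions' results are correlated, for which the plan gives no basis.

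Finally, the source of the functional ROIs is a cited study that is not available here, so what the authors meant by dACC cannot be confirmed.

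**Conclusion.** The point holds as an internal contradiction in an analysis specification. The Aim 2 sentence in Section 9.2 names a cingulate region that differs from the one in the Aim 2 hypothesis, the power text, the target-engagement ROIs and the Aims 1 and 5 model. Taken literally, it does not test the cingulate part of the hypothesis, and it relies on a region with no stated hypothesis, activation ROI or contrast.

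The size is limited: one of the two regions in one aim. No numerical effect on error rate or power can be attached to it from the documents. The conclusion assumes that dACC stands for the dorsal anterior cingulate, as the connectivity paragraph suggests. If it is a slip for rACC, which is the likelier explanation, the intended analysis is sound and only the text is wrong. A reader might infer that the decision to start R33 was made on the wrong region. The documents say otherwise, since that decision rests on the CN and rACC ROIs.

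**What to change.** In the Aim 2 paragraph of Section 9.2, replace CN and dACC with the right CN in reward anticipation and the rACC in reward outcomes. State that both use the functional ROIs and MID contrasts of the go/no-go paragraph. This also restores the laterality that the sentence now omits. Add that the hierarchical linear model applies to the same two outcomes.

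If the dACC was truly intended, state its hypothesis with direction, its ROI and its contrast. Label it separately from the Aim 2 hypothesis in Section 4.1, and still provide an rACC analysis for that hypothesis.

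Section 4.1 records that the study has moved on from R61 to R33, so the Aim 2 report should also state which cingulate ROI was or will be analysed. The cost is an edit to one paragraph. No new data, scans or participants are needed.
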